7.2.8 MRI visit 2 (Week 6 ± 5 days)

Participants will return to the CNMRR Center for their final MRI scan after refraining from smoking for 14 hours prior to the visit.

For the final study visit, participants will complete the following activities:

1. Return all (empty and full) cigarettes packs
2. Penn State CNMRR MRI safety and Scent Ratings (post MRI)
3. Urine collection for cotinine analysis and pregnancy determination: Obtain urine and process pregnancy test for women of child bearing age (have had a period in the past 12 months) who have not had a hysterectomy
4. Saliva collection for potential cotinine analysis, micro RNA (miRNA) biomarker analysis, and use in future research.
5. Exhaled carbon monoxide will be measured using a hand-held monitor.
6. Computerized REDCap Survey Questionnaires (nicotine withdrawal, smoking urges, craving)
7. The MRI technologist will first review the MRI safety sheet and determine that it is safe for the participant to be scanned. If safe, participants will complete a one-hour MRI scan.

Time commitment: 2 hours

7.2.7 Text message with quit attempt survey (Week 18 ± 5 days)

Participants will receive a text message with a REDCap survey link inquiring about current smoking status and past 12-week quit attempts. Participants will be sent a second text message if they do not complete the survey within 72 hours of the first message. The study coordinator will call participants who are unwilling or unable to receive text messages to complete the survey.

7.3 Duration of Participation

Participants who complete all study visits in the ideal time frame will be in the study for 18 weeks. The majority of participants are expected to complete the study in 7 to 18 weeks.

7.4 Test Article(s) (Study Drug(s) and/or Study Device(s))

7.4.1 Description

Participants will be provided with research cigarettes that have a similar nicotine content to current commercially available cigarettes (11.6mg) or a very low nicotine content (0.29mg). Participants will have a 0.67 probability of being assigned to the very low nicotine content research cigarette and a 0.33 probability of being assigned to the usual nicotine content cigarette. The cigarettes will be managed by an unblinded study member.

7.4.2 Treatment Regimen

Participant will be asked to smoke their assigned study research cigarettes (11.6 mg or 0.29 mg nicotine content) for 6 weeks.

7.4.3 Method for Assigning Subject to Treatment Groups

Participants will be randomized to one of two experimental conditions based on a blocked randomization sequence stratified by gender. A 2:1 randomization strategy will be used, resulting in 0.67 probability of being assigned to the very low nicotine cigarette, and a 0.33 probability of being assigned to the usual nicotine cigarette. The randomization key will be stored in REDCap and will be accessible only to unblinded study members and the faculty project mentor. The principal investigator will not have access to the code to ensure blinding.

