7.0 Study Design and Procedures

7.1 Study Design

This is a two-arm, randomized, double-blind parallel group trial. Smokers will be randomly assigned to smoke very low nicotine content (VLNC) (n=50) or normal nicotine content (NNC) (n=25) SPECTRUM cigarettes for 6 weeks. Participants and study staff will be blind to the experimental cigarette allocation until the study is complete. The groups will be stratified by gender.

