8.2 Sample size determination

Dependent smokers of low SES (n=75) will be recruited for the current study through the TCORS study call center (protocol #2213). Two-thirds of the sample (n=50) will be randomized to the VLNC group to maximize power for the within-subjects repeated measures analyses while still allowing for an analysis of between-subjects effects. There is not currently an accepted method for determining sample size a priori for repeated measures fMRI designs. With repeated measures behavioral data, to detect a medium effect size ($f=0.25$) with 80% power and a Type I error rate of .05, a sample size of 28 is required to detect within-subjects effects, 86 for between-subject effects, and 28 for within x between interactions. The estimate for detecting such effects with fMRI is likely somewhat higher; however, my mentors have found within-subject effects with similar tasks that will be used for this project with comparable sample sizes; smoking cue reactivity (n=22)⁶¹ card-guessing task (n=44)⁵, and the n-back task (n=33)⁶². Thus, we estimate that the current design will have adequate power to detect small to medium within-subjects effects and medium to large between-subjects effects. The design will serve as pilot data to determine sample size for future studies. TCORS found retention rates of 85% for their 18-week trial and a prior 6-week VLNC intervention found retention rates at 92%.⁴⁹ Retention for the proposed study will likely be higher given frequent contact with participants (3-week visit and two phone-check-ins); however, with a conservative estimate of 80% retention and adequate compliance, the final sample size (n=60) would still be adequately powered. We will recruit until we have 75 study completers. It is likely that participants that complete informed consent at the remote screening will be ineligible. Therefore, we expect around 90 participants to complete informed consent and 75 to complete the entire study.

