8.3 Statistical methods

Data Analysis. Images will be preprocessed using FSL, including registration to high resolution anatomical images and standard space, brain extraction, slice timing correction, spatial and temporal smoothing, intensity normalization, physiological noise correction, and motion correction for 6 motion parameters and artifacts identified via ICA-AROMA.⁶³ For task-based images, contrasts of the relevant conditions will be determined during first level analyses as described above and averaged across multiple runs for each participant.

Aim 1: Examine the longitudinal effect of VLNC cigarettes on changes in task-related functional neural activation within brain circuitry associated with incentive salience valuation and executive function.

Treatment-related within-subject and between-subject changes in BOLD activation during all fMRI tasks will be assessed in linear mixed-effects models using FSL software. Whole-brain analyses and ROI analyses based on pre-determined salience and executive control circuitry will be conducted. Paired t-tests will identify anatomical regions showing statistically significant differences from baseline to 6-week scans across groups.

Aim 2: Assess the longitudinal effect of VLNC cigarettes on changes in effective (directional) connectivity between incentive salience and executive control brain circuitry. Dynamic causal modeling (DCM) using SPM12 software will measure effective connectivity between ROIs in the incentive salience and executive control networks.⁶⁴ Specifically, DCM identifies models with task-specific increases in the dependence of the BOLD activity timecourses between a priori selected nodes and estimates directionality. We expect that the use of the VLNC cigarettes will strengthen the influence of the executive control over incentive salience circuitry during the smoking Go/NoGo and temporal discounting tasks. ROIs will be selected a priori for these analyses. Given the novelty of the odor cue reactivity task, active brain circuitry identified in Aim 1 will be included as nodes in the DCM model to test the hypothesis that non-smoking reward circuitry will exert an increasing influence over smoking salience circuitry. Connectivity estimates from the models will be included in a mixed-effects ANOVA to determine between-subjects and within-subject effects across the trial.

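### Randomisation is stratified by gender but no planned VLNC–NNC comparison includes a gender term; if gender predicts the analysed quantity, those comparisons are conservative and lose power

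*Combined protocol and SAP*

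**What the plan says.** Gender is the stratification factor in two places. Section 7.1 says "The groups will be stratified by gender", and Section 7.4.3 says "Participants will be randomized to one of two experimental conditions based on a blocked randomization sequence stratified by gender". On allocation, Section 7.4.3 adds "A 2:1 randomization strategy will be used", which gives 50 VLNC and 25 NNC.

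Section 8.3 describes the Aim 1 arm comparison in one sentence: "Treatment-related within-subject and between-subject changes in BOLD activation during all fMRI tasks will be assessed in linear mixed-effects models using FSL software". For Aim 2, connectivity estimates go into a mixed-effects ANOVA with between- and within-subject effects. The Aim 4 analysis is in Section 1.1: a two-way repeated-measures ANOVA of miRNA in the two groups over three time points. No gender term is named in any of these. The only covariate named anywhere is concomitant medication (Section 7.4.6.5).

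**The concern.** Stratified allocation balances gender across the arms, so gender differences add little or nothing to the real sampling error of the arm difference. A model without gender still counts that variation as residual noise. Its standard error then exceeds the real one, the type I error falls below 5%, and the precision that stratification was meant to buy is lost. With 25 controls planned, and about 20 if 60 participants remain, there is reason not to give this away. There is also some reason to expect gender to matter: Section 7.2.1 scores the smell test against gender norms, and Section 1.2 makes neural reactivity to tobacco odor a primary endpoint. That does not show that gender predicts change, but it makes gender a sensible term to prespecify.

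**Working it through.** **1. The plan's own sample-size figure.** Section 8.2 assumes f = 0.25, 80% power and α = 0.05, and concludes: "a sample size of 28 is required to detect within-subjects effects, 86 for between-subject effects, and 28 for within x between interactions". It states neither the number of measurements m nor their correlation ρ. With two equal groups, m = 3 and ρ = 0.5 (both assumed), the noncentral F distribution gives:

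- Between: λ = N f² m / [1 + (m − 1)ρ] = 86 × 0.0625 × 3 / 2 = 8.06, df 1 and 84, power 80.1%.
- Within and interaction: λ = N f² m / (1 − ρ) = 28 × 0.0625 × 3 / 0.5 = 10.5, df 2 and 52, power 81.2%.

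So 28/86/28 reproduces. It contains no covariate adjustment and says nothing about gender.

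**2. Standard error of the arm difference in change.** Let R² be the within-arm share of change-score variance explained by gender; the documents give no value, so a range is used. Work in units of the SD of change that remains after gender. With gender balanced at 50:25, the true standard error is √(1/50 + 1/25) = 0.245. A model without gender reports 0.245 / √(1 − R²).

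**3. Power.** Take a true effect of 0.69 residual SD, chosen because it gives about 80% power with gender in the model. The critical t on 73 df is 1.993, so power without gender ≈ Φ[(0.69 − 1.993 × reported SE) / 0.245]. At R² = 0.20 this is Φ[(0.69 − 1.993 × 0.274) / 0.245] = Φ(0.59) = 72%.

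| R² | SE ratio | Reported SE | Type I error without gender | Power without gender | Power with gender | Loss (points) |
|---|---|---|---|---|---|---|
| 0 | 1.000 | 0.245 | 5.0% | 79.5% | 79.5% | 0 |
| 0.05 | 1.026 | 0.251 | 4.4% | 78.0% | 79.5% | 1.5 |
| 0.10 | 1.054 | 0.258 | 3.9% | 76.3% | 79.5% | 3 |
| 0.20 | 1.118 | 0.274 | 2.8% | 72.2% | 79.5% | 7 |

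The loss depends somewhat on the set-up:

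- *Slight imbalance, 50:25.* A simulation (10,000 runs per setting) had 25 women of 50 in VLNC and 13 of 25 in NNC. Power without and with gender was 76.7% and 79.5%, 74.8% and 79.6%, and 69.0% and 79.3%, so losses of about 3, 5 and 10 points. These exceed the table because the imbalance of 0.02 also pulls the unadjusted estimate down. The opposite imbalance would push it up.
- *Effect of 0.5 total SD, 50:25.* Power is about 52% without gender, against 54.2%, 56.5% and 61.5% with it: about 2, 4 and 9 points.
- *Effect of 0.69, 40:20, exactly balanced.* Simulated power is 68.5% and 70.6%, 65.9% and 69.5%, and 60.4% and 69.7%: about 2, 4 and 9 points.

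**4. Change against level.** Each participant's baseline is subtracted, so a gender gap that is the same at both scans cancels. Simulated with a 0.8 SD gap at both scans and no effect on change, power at 50:25 is 79.6% with or without gender. Only a gender-by-time effect counts towards R² in this contrast. For an arm main effect averaged over visits, which the Aim 2 and Aim 4 ANOVAs also produce, a constant gap does not cancel and stays in the error term.

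**5. Which term is needed.** In a repeated-measures model, a gender main effect is constant over visits, so it cannot absorb variance in change. In one simulated 50:25 two-scan dataset where gender did affect change, the arm-by-time standard error was 0.200 with no gender term, 0.200 with a gender main effect and 0.182 once gender-by-time was added. In a change-score model, a plain gender covariate already does that job.

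**The case against.** The strongest reply is that Section 8.3 is silent on gender and does not exclude it. It lists no covariates at all, although Section 7.4.6.5 promises medication covariates, so it is not a full model specification. This stands for Aims 1 and 2. It is weaker for Aim 4, where a two-way ANOVA of arm and time leaves no place for a third factor. An open choice is itself worth closing before the data are seen.

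A second reply is that no loss has been shown. A reader might infer from the stratification alone that the standard errors are too wide and that power is lost. The documents do not support that: nothing in them says gender predicts change in BOLD signal, connectivity, dependence or miRNA, and a stable gender difference costs the longitudinal contrast nothing. This stands in full.

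Third, the error is only conservative: it does not inflate false positives. Section 8.2 treats the design partly as pilot work and, on its own assumptions, asks for only 28 participants for the interaction. For effects that large the power loss would be smaller than in the table. The 86 it asks for on between-subject effects already exceeds both the planned 75 and the 60 of which it says "with a conservative estimate of 80% retention and adequate compliance, the final sample size (n=60) would still be adequately powered".

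Finally, the argument does not reach every test in Section 8.3. The Aim 1 paired t-tests pool the groups, and the Aim 3 tests are associations. Neither compares arms, so neither is affected.

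**Conclusion.** The point holds in conditional form. The planned VLNC–NNC comparisons in Aims 1, 2 and 4 do not name the randomisation stratum. If gender predicts the analysed quantity, they will have standard errors that are too wide and will lose power. For gender explaining 0%, 5%, 10% or 20% of change-score variance, the standard error is about 0%, 3%, 5% or 12% too wide. The power loss at 50:25 is about 0, 2–3, 3–5 or 7–10 points. Those shares are assumptions, and the power figures also assume effects of 0.5 to 0.69 SD and near-balanced gender. Confidence is high on the omission and the direction, and low on the size. It would be wrong to read this as a certain loss, or as a threat to the validity of a positive result. It is a free improvement.

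**What to change.** Add to Section 8.3: *All VLNC–NNC comparisons in Aims 1, 2 and 4, and of change in dependence measures, adjust for the randomisation stratum (gender): as a covariate in change-score models, and as gender plus gender-by-time in repeated-measures models.*

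The interaction must be named, because a gender main effect alone would leave the arm-by-time standard error unchanged. The two-way description of the Aim 4 ANOVA in Section 1.1 should be brought into line. The Aim 1 paired t-tests and the Aim 3 association tests need no change on this account.

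The cost is one sentence and one or two degrees of freedom: one in a change-score or two-scan contrast, and two for gender-by-time over the three time points of Aim 4. With 60 to 75 participants this is negligible, and at R² = 0 power is practically unchanged (79.4% without gender and 79.3% with it in simulation).

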7.4.4 Subject Compliance Monitoring

Participants will track the number of cigarettes they smoke each day in the REDCap surveys sent to them via text message and using a paper tally tracking log. Participants will be given detailed instructions on how to complete the logs and they will be reminded at each study contact to only use the research cigarettes they have been given. Questions will be asked at each contact to review their log and verify how many cigarettes they are smoking each day. Participants will also be asked to self-report their other tobacco use including products such as cigars, pipes, chew, snus, dip, hookah, electronic cigarettes and dissolvable tobacco. Exhaled carbon monoxide measurements, urine, and saliva will be taken at each contact to verify smoking intensity and cotinine levels.

7.4.5 Blinding of the Test Article

Cigarette cartons will arrive to the PI's laboratory with a packaging slip that provides information about the cartons in the shipment which includes the NRC code nicotine content, RTI log carton bar code number and a batch/lot number. Each carton is labeled with the RTI Log number. The RTI Log number and corresponding NRC code will be carefully recorded by the unblinded study member in the REDCap randomization database. Individual packs do not contain any identifiable information; however with each shipment a set of labels indicating the RTI log numbers are also included. At the time of dispensing, the unblinded study team member will remove the RTI log number from the carton. If less than a full carton is dispensed to a participant, the remaining packs in the carton will be labeled with the RTI log number labels. At the time each pack is dispensed, the RTI log number label will be removed and maintained by the unblinded study team member as confirmation that the correct product was dispensed to the subject at the visit.

7.4.6 Receiving, Storage, Dispensing and Return

7.4.6.1 Receipt of Test Article

Experimental cigarettes will be provided free of charge to the investigators via the NIDA Drug Supply Program (see Notice: NOT-DA-13-002). Cartons (10 packs/carton) with packs of 20 cigarettes/pack will be received from the Research Triangle Institute in North Carolina.

7.4.6.2 Storage

At Penn State Hershey, cigarettes will be stored in locked, -20 freezers that are maintained by the PI's Department. Standard laboratory protocols for freezer temperature control monitoring and recording will be followed. Prior to cigarette assignment, the cigarettes may be stored unfrozen for a period of time up to 3 weeks.

7.4.6.3 Preparation and Dispensing

Assignment: When a new participant is randomized, they will receive the packs labeled with their study ID number indicating that these are research cigarettes.

Preparation: Once the cigarettes are received, they will be blinded by the unblinded study member. At the time of dispensation, the unblinded study member will prepare a bag of cigarette packs labeled with the participant ID number and indicating that they are research cigarettes. The RTI log number labels will be removed from the packs/cartons at the time of preparation for dispensing.

Where: All receiving, sorting, blinding of the initial study product will be done by an unblinded member of the study team in a designated space for this study at Penn State Hershey. Dispensing of product to study participants will occur at the Center for NMR Research where participants will complete their MRI visits.

Dispensing: Cigarette packs containing 20 cigarettes will be prepared by the unblinded study member prior to a participant's in person visit. All packs will be given to participants in the original packaging. Each individual pack of cigarettes will have a label with the participant ID number and a list of possible nicotine doses the cigarettes may contain. The coordinator will give the cigarettes to the participant at their second visit. The number of packs dispensed will be determined by the self-reported number of cigarettes per day they smoke determined by the baseline week cigarette log. Participants will be provided with 125% of the cigarettes necessary for each week of usual smoking. Participants will be able to smoke as many or as few cigarettes as they choose and will be required to return all packs (empty and full) at the next visit.

7.4.6.4 Return or Destruction of the Test Article

The unblinded study member will track all receipt, dispensing, and blinding of cigarettes for the duration of the project. The study coordinator will track all dispensing of blinded cigarettes for the duration of the project. The unblinded study member will have access to receipt and dispensation logs to create reconciliation reports on an ongoing basis. Participants will be instructed to bring all research cigarette packs to the next visit, regardless of whether they are empty, unopened or partially used. The number of unused packs will be recorded and returned to the study participants at the end of the visit. We will not ship experimental cigarettes back to the NIDA Drug Supply Program. Empty packs dispensed to and returned by study participants will be destroyed once the usage information has been documented.

7.4.6.5 Prior and Concomitant Therapy

Concomitant medication use will be collected regularly throughout the trial to serve as covariates during analysis and to monitor participant health conditions. Participants taking varenicline, bupropion or nortriptyline as a smoking

cessation medication in the prior month will be excluded from the study. Participants taking bupropion or nortriptyline for depression management and who expect to continue use of the medication throughout the trial will be eligible to participate. Additionally, participants who are prescribed bupropion or nortriptyline for depression management at any point during the study will be eligible to continue with the study. Medications related to certain medical conditions that are exclusions to the study, such as COPD and current heart conditions, will serve to alert the study staff of the presence of these conditions during screening. Once the participant is entered into the randomized double blind phase of the study, there are no medications that will interfere with the participant's ability to participate.

8.0 Subject Numbers and Statistical Plan

8.1 Number of Subjects

We expect to enroll approximately 90 participants in order to retain 75 study completers.

8.2 Sample size determination

Dependent smokers of low SES (n=75) will be recruited for the current study through the TCORS study call center (protocol #2213). Two-thirds of the sample (n=50) will be randomized to the VLNC group to maximize power for the within-subjects repeated measures analyses while still allowing for an analysis of between-subjects effects. There is not currently an accepted method for determining sample size a priori for repeated measures fMRI designs. With repeated measures behavioral data, to detect a medium effect size ($f=0.25$) with 80% power and a Type I error rate of .05, a sample size of 28 is required to detect within-subjects effects, 86 for between-subject effects, and 28 for within x between interactions. The estimate for detecting such effects with fMRI is likely somewhat higher; however, my mentors have found within-subject effects with similar tasks that will be used for this project with comparable sample sizes; smoking cue reactivity (n=22)⁶¹ card-guessing task (n=44)⁵, and the n-back task (n=33)⁶². Thus, we estimate that the current design will have adequate power to detect small to medium within-subjects effects and medium to large between-subjects effects. The design will serve as pilot data to determine sample size for future studies. TCORS found retention rates of 85% for their 18-week trial and a prior 6-week VLNC intervention found retention rates at 92%.⁴⁹ Retention for the proposed study will likely be higher given frequent contact with participants (3-week visit and two phone-check-ins); however, with a conservative estimate of 80% retention and adequate compliance, the final sample size (n=60) would still be adequately powered. We will recruit until we have 75 study completers. It is likely that participants that complete informed consent at the remote screening will be ineligible. Therefore, we expect around 90 participants to complete informed consent and 75 to complete the entire study.

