1.2 Primary Study Endpoints

Changes in neural reactivity to tobacco odor and changes in smoking dependence.

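### Section 8.2 claims adequate power from medium between-subject effects upward with 75 completers, but its own figure for a medium effect is 86, and the n=60 reassurance names no effect

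*Combined protocol and SAP*

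**What the plan says.** Section 8.2 sets medium at f=0.25 and, for repeated-measures behavioural data with 80% power and a type I error rate of .05, states that "a sample size of 28 is required to detect within-subjects effects, 86 for between-subject effects, and 28 for within x between interactions". It adds that fMRI probably needs somewhat more. It then concludes that the design has "adequate power to detect small to medium within-subjects effects and medium to large between-subjects effects".

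On attrition, it takes 80% retention with adequate compliance and says "the final sample size (n=60) would still be adequately powered", without naming an effect type or size. The next sentence reads "We will recruit until we have 75 study completers", and section 8.1 agrees: "We expect to enroll approximately 90 participants in order to retain 75 study completers".

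On design and analysis, section 7.4.3 says "A 2:1 randomization strategy will be used". For Aim 2, section 8.3 puts the connectivity estimates into a "mixed-effects ANOVA to determine between-subjects and within-subject effects across the trial". Section 1.2 gives the primary endpoints as "Changes in neural reactivity to tobacco odor and changes in smoking dependence".

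**The concern.** The required number for a medium between-subject effect (86) is larger than the number the plan intends to have (75) and larger still than its fallback (60). Yet the paragraph counts medium between-subject effects among those it can detect. The precedents it cites in support are described as within-subject findings, so they do not fill the gap.

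The n=60 sentence has a second problem. By the plan's figures it could be true for within-subject and interaction effects (28 each) but not for the between-subject effect (86), and the reader is not told which is meant. It also treats 75 as the number who start (0.80 × 75 = 60), whereas section 8.1 and the following sentence make 75 the number who finish.

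At stake is how a null between-subject result would be read. Such effects are part of the Aim 2 ANOVA, and a reader relying on section 8.2 would credit that test with power it does not have.

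**Working it through.** **Direct comparison.** No model is needed for the contradiction: 86 > 75 > 60.

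**Inputs.** From section 8.2: f=0.25, 80% power, two-sided 5% level, N=75 and N=60. From section 7.4.3: 2:1 allocation. From section 2.3: two scans, baseline and 6 weeks. The number of occasions m and the correlation ρ behind 28/86/28 are not stated, so I solved for them.

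**Formulas** (repeated-measures ANOVA, noncentral F, sphericity assumed, two groups):
- Between: λ = f²·N·m / (1 + (m−1)ρ), with 1 and N−2 degrees of freedom.
- Within and interaction: λ = f²·N·m / (1−ρ), with m−1 and (N−2)(m−1) degrees of freedom.

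**Reproducing the plan's figures.** Take m=3, ρ=0.5.
- Between, N=86: λ = 0.0625 × 86 × 3 / 2 = 8.06, power 80.1%. N=84 gives 79.2%, so 86 is the smallest even N.
- Within and interaction, N=28: λ = 0.0625 × 28 × 3 / 0.5 = 10.5, power 81.2%. N=26 gives 77.8%, so 28.

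In a search over 2 to 4 groups, 2 to 5 occasions and ρ from 0 to 0.95 in steps of 0.05, only two groups, m=3 and ρ=0.5 gave all three figures. Three occasions also match the behavioural measures, which are collected at Remote visits 1, 2 and 3.

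**Between-subject power at the planned numbers** (m=3, ρ=0.5). With f fixed, allocation does not enter. If instead a 0.5 SD difference is held fixed, 2:1 allocation multiplies λ by 4 × (2/3) × (1/3) = 8/9.

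| N | λ, f=0.25 fixed | Power | λ, 0.5 SD fixed at 2:1 | Power |
|---|---|---|---|---|
| 75 | 7.03 | 74.4% | 6.25 | 69.4% |
| 60 | 5.63 | 64.5% | 5.00 | 59.4% |

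For an assumed ρ of 0.3 to 0.7 (f fixed, m=3), power runs from 83.3% down to 66.6% at 75, and from 74.1% down to 56.7% at 60.

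**Detectable between-subject size at 80% power** (m=3, ρ=0.5): f=0.268 at 75 and 0.300 at 60. With the 8/9 factor applied, on the scale where 0.5 SD equals 0.25, these become 0.284 and 0.319. Both scales describe the same raw difference: 2 × 0.284 = 0.57 SD and 2 × 0.319 = 0.64 SD.

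**Large effects.** At f=0.40 with the 8/9 factor, power is 97.7% at 75 and 94.0% at 60.

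**What f=0.25 means for arm-by-time.** With two equal arms and two scans, an interaction f of 0.25 is a between-arm difference in change of 4 × 0.25 = 1.0 SD, in units of the single-occasion SD. The SD of change is √(2(1−ρ)), and the noncentrality is the difference divided by SD × √(1/n₁ + 1/n₂). At ρ=0.5 and 40:20, a 0.5 SD difference gives 0.5 / √0.075 = 1.83. Power for one uncorrected two-sided test:

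| Difference in change | N (split) | ρ=0.3 | ρ=0.5 | ρ=0.7 |
|---|---|---|---|---|
| 1.0 SD | 60 (40:20) | 85.9% | 94.8% | 99.6% |
| 0.5 SD | 60 (40:20) | 33% | 44% | 64% |
| 0.5 SD | 75 (50:25) | 40% | 52% | 74% |

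**The case against.** The strongest reply is that the claim is a hedged range in a study described as pilot work, and that only its lower end fails. The detectable f at 75 (0.27) lies just above medium and far below 0.40. This stands as a limit on the size of the problem. It does not remove it, because the paragraph gives medium a number and that number can be checked.

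Second, the hypotheses do not rest on a between-subject main effect, which averages over occasions including the one before treatment. Aims 1 and 2 and the primary endpoints are changes, and the Aim 2 ANOVA sentence is where the main effect clearly enters. This also stands and is why the consequence is limited.

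Third, a lower correlation could rescue the claim. With three occasions and f fixed, 75 suffices at ρ of 0.37 or less and 60 at 0.19 or less. But the plan's requirement would then not be 86; at ρ=0.3 it would be 70. The rescue contradicts the stated figure.

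Fourth, n=60 may mean the compliant, analysable subset of 75 completers. That is possible, but the text does not say so.

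Two inferences go too far in opposite directions. A reader might conclude that 86 is miscalculated or that the whole trial is too small. The documents do not support this: 86 reproduces, and the aims do not depend on that effect. A reader might also take the 28 for interactions as showing that the arm-by-time comparison is safe at 60. That holds only for a difference in change of about 1.0 SD, not for 0.5 SD.

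**Conclusion.** The point holds for the lower end of the between-subject claim. By the plan's own figure, 75 completers do not give 80% power for a medium between-subject effect, and 60 fall further short: 74.4% and 64.5% with f fixed, or 69.4% and 59.4% with 0.5 SD fixed at 2:1. The direct contradiction (86 against 75 and 60) rests on no assumption. The percentages rest on three occasions, correlation 0.5 and sphericity, and apply to behavioural data; the plan itself expects fMRI to need more.

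The n=60 statement cannot cover a medium between-subject effect, and it supports no general claim of adequacy for arm-by-time effects. The unstated occasions and correlation are missing detail, not an error in themselves, since the figures can be recovered. This should be corrected, but it does not undermine the aims or the primary endpoints.

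**What to change.** Reword section 8.2:

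- Replace the medium-to-large between-subject claim with the detectable size at 80% power: about f=0.27 at 75 and 0.30 at 60 with f fixed (0.28 and 0.32 on the 0.5 SD-equivalent scale at 2:1). State three occasions and correlation 0.5 as assumptions, once the authors confirm them, and say which scale applies.
- State that the n=60 sentence does not cover a medium between-subject effect. If it is kept for arm-by-time effects, express the effect as a difference in change, with the correlation range and the single uncorrected test made explicit: 1.0 SD has 86% to 99.6% power at 40:20, whereas 0.5 SD has about 33% to 64% at 60 and 40% to 74% at 75. Make no general claim of adequacy.
- Reconcile 60 (80% of 75) with recruiting to 75 completers, by saying whether 75 start or finish, or whether 60 is an analysable subset.
- Keep the existing caution about fMRI.

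The cost is a few sentences and a less favourable power statement. Sample size, recruitment and procedures do not change.
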